## **Methodology**

**Sample:** The study will be carried out with adolescents in the second and third years of high school in Bizkaia (Spain). The necessary estimated sample size is 500, under a small, anticipated effect size (0.2), a statistical power of 0.8, and a probability level of 0.05. In anticipation of a loss of participants during the follow-ups, the sample size will be increased to 600. Inclusion criteria include adequate reading comprehension and parental and self-informed consent.

**Design and Procedure:** A randomized controlled trial with two groups will be used. Randomization will be done by clusters, using the classroom as the unit. First, the schools will be selected according to their characteristics. Then, for each school and grade, half of the classrooms will be randomly assigned to the experimental condition (values alignment) and the other half to the control condition (traditional educational intervention). Participants will complete an online assessment protocol using Qualtrics, which will be composed of different questionnaires at three time points: (1) pretest (immediately before the intervention), (2) posttest (one week after the intervention), and (3) a three-month follow-up. The study has the approval of the Ethics Committee of the University of Deusto. The trial will be registered on ClinicalTrials.gov.

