**Interventions:** The experimental group will receive the values alignment intervention (Bryan et al., 2016). This includes: (1) reading materials, such as recent journalistic works that expose the deceptive and manipulative marketing practices of food companies and the harmful effects of these practices on society, with particular emphasis on harm to young children and the economically disadvantaged. Stories from other young people will also be included in order to contribute to the perception of widespread outrage and to suggest how that outrage can be channeled into taking a stand against the injustice perpetrated by food companies by eating less unhealthy or healthier food, (2) writing exercises, such as a story with a brief statement of what the participants would tell a younger child about the ads, and (3) an interactive activity, called "Make It Real" in which they are shown pictures of food ads and allowed to write and draw about them, making whatever changes (e.g., crossing out and substituting words) they feel necessary to make the ad "real" (i.e., no longer misleading). The control group will receive a traditional educational intervention on nutrition and physical exercise. This will be of the same duration and will also include reading and writing exercises.

**Measurements:** Healthy and unhealthy food intake will be measured at pretest, posttest, and three-month follow-up using the questionnaire developed by Stok et al. (2015). It consists of

four items that provide an index of unhealthy eating. In addition, according to the content addressed in the intervention sessions in the posttest and three-month follow-up, two attitudinal variables will be evaluated: (1) the alignment of healthy eating habits with the values of adolescents using seven items from Bryan et al. (2019), and (2) the social attractiveness of healthy eating using three items from Bryan et al. (2019), and answered on a five-point scale. Finally, some individual characteristics will be measured through an ad hoc questionnaire: gender, age, socioeconomic status (education and parental profession), height, and weight (to determine BMI).

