**Statistical Analysis:** To evaluate the effect of the intervention on the repeated measures of the dependent variables, a multilevel analysis with MPLUS-8.8 will be used. This will include repeated measures at level one (e.g., healthy and unhealthy food intake), adolescent variables at level two (assigned intervention and potential moderators), and the classroom at level three. It will be determined whether the intervention explains the slope of change of the dependent variables (intervention  $\times$  time interaction). For moderation effects, triple interaction terms will be created using dummy variables or z variables, depending on the nature of the variables. To assess whether the effect of the intervention on healthy and unhealthy food intake is mediated by the attitudinal variables, a structural equation model with a bootstrapping procedure will be estimated ( $N = 10,000$  samples). For the handling of missing values, the full information maximum likelihood method will be used as a general approach, although, depending on the nature of the missing value patterns, other techniques (e.g., multiple imputations or use of auxiliary variables) may be used.

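### The attitude models do not commit to using pretest food intake, a baseline value the trial already collects (minor, free improvement)

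*Combined protocol and SAP*

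**What the plan says.** Under Measurements (Methodology), the two kinds of outcome have different schedules. For intake: "Healthy and unhealthy food intake will be measured at pretest, posttest, and three-month follow-up". For values alignment and social attractiveness: "in the posttest and three-month follow-up, two attitudinal variables will be evaluated". Because both statements stand in one paragraph, the natural reading is that attitudes have no pretest. The same paragraph adds that "some individual characteristics will be measured through an ad hoc questionnaire: gender, age, socioeconomic status", along with height and weight, but does not say at which occasion.

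Under Statistical Analysis, the multilevel model has repeated measures at level one, then "adolescent variables at level two (assigned intervention and potential moderators), and the classroom at level three". Project Objectives names the moderators as socioeconomic status, gender and BMI. Pretest intake is not listed as a predictor of attitudes. For missing values, "the full information maximum likelihood method will be used as a general approach", although, depending on the patterns found, "other techniques (e.g., multiple imputations or use of auxiliary variables) may be used". No auxiliary variable is named.

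Under Sample, 500 pupils are required for an effect of 0.2, raised to 600 for loss to follow-up. No loss rate is given.

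**The concern.** One missing-data rule covers outcomes with different amounts of baseline information. A pupil lost before the posttest still contributes a pretest value to an intake model. The same pupil contributes nothing to a model that contains only attitude scores, assigned arm and moderators. FIML uses only the variables placed in the likelihood, so it cannot draw on a pretest intake value that is left out.

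What is at stake is mainly the attitude comparison in objective 3. If pretest intake predicts attitude, omitting it gives up precision. If early loss also depends on intake, and does so differently in the two arms, the attitude contrast shifts although the variable behind the loss was measured.

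**Working it through.** **Inputs from the documents.** Effect 0.2 (metric not stated; taken here as SD units). Required 500, recruited 600, so the allowance is 600 - 500 = 100, and 100/600 = 16.7%. About 30 classrooms (Budget), so 600/30 = 20 pupils each. The plan gives no figure for missing attitude data, so there is none to reproduce. The derivation of the 500 does not affect this point.

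**Assumptions, not in the documents.** Correlation r of pretest unhealthy intake with attitude between -0.2 and -0.5; the loss patterns below; the classroom intraclass correlations (ICC) below.

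**Step 1: do pupils without attitude scores contribute?** In a simulated trial of 300 per arm, 237 control and 245 experimental pupils had at least one attitude score; 221 and 228 had both. FIML on the two attitude scores gave the same means with or without the pupils who had neither: -0.007809 and 0.011369 (control), 0.261480 and 0.192547 (experimental). Strict completers gave different control means, 0.040361 and 0.036376. So FIML uses pupils with at least one attitude score, which is more than completers.

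**Step 2: precision.** With intake as a covariate and clustering ignored, the SE is multiplied by sqrt(1 - r²):

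- |r| = 0.2: sqrt(0.96) = 0.980, a cut of 2.0%
- |r| = 0.3: sqrt(0.91) = 0.954, a cut of 4.6%
- |r| = 0.4: sqrt(0.84) = 0.917, a cut of 8.3%

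This needs no dropout. With the 16.7% loss pattern of Step 3 and r = -0.4, simulation gave 0.0898 unadjusted and 0.0833 with intake as a covariate: 1 - 0.0833/0.0898 = 7.2%. Modelling intake jointly but leaving its mean free in each arm gave 0.0894, almost no gain.

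With clustering, suppose intake varies between pupils but not between classrooms. The factor becomes sqrt(1 - r²/DE), where DE = 1 + 19 x ICC. At |r| = 0.4:

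- ICC 0.02: DE 1.38, sqrt(1 - 0.16/1.38) = 0.940, a cut of 6.0%
- ICC 0.05: DE 1.95, sqrt(1 - 0.16/1.95) = 0.958, a cut of 4.2%
- ICC 0.10: DE 2.90, sqrt(1 - 0.16/2.90) = 0.972, a cut of 2.8%

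**Step 3: bias.** Let loss in the experimental arm differ above and below median pretest unhealthy intake, and let control loss be unrelated to intake. The half-normal mean is 0.798. The mean standardised intake of experimental pupils who stay is 0.798 x 0.5 x (stay above - stay below) / (overall stay). Multiplying by r gives the bias.

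- 5% lost (8% above, 2% below): 0.798 x 0.5 x (0.92 - 0.98)/0.95 = -0.025. For r = -0.3 to -0.5 the bias is 0.008-0.013 SD, or 4-6% of 0.2.
- 16.7% lost (25% above, 8.3% below): 0.798 x 0.5 x (0.75 - 0.917)/0.833 = -0.080. The bias is 0.024-0.040 SD, or 12-20% of 0.2.

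At r = -0.4 the formula gives 0.232 for a true 0.20 in the second case; two simulations gave 0.229 and 0.235. In the 5% case it gives 0.210, and simulation 0.211. With pretest intake in the model the estimate returned to about 0.20.

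**Step 4: when does the bias vanish or grow?** With 16.7% lost per arm, and loss either random or dependent on intake equally in both arms, simulation gave about 0.20 with or without pretest intake. A steeper dependence in one arm only (log-odds 1 per SD) gave about 0.23, 0.24 and 0.27 at |r| = 0.2, 0.3 and 0.5. Opposite dependence in the two arms gave about 0.26, 0.29 and 0.34. Including pretest intake returned about 0.20 in every case.

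**The case against.** The strongest reply is that the plan already names the remedy: auxiliary variables and multiple imputation are both allowed. That largely stands, and it makes this a matter of commitment rather than of a wrong method. It is not a complete answer, because no variable or trigger is named and missing-value patterns alone cannot show that conditioning on intake is unnecessary.

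A reader might infer four stronger things that the documents do not support.

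- *That FIML reduces to a completer analysis.* It keeps anyone with either attitude score (Step 1).
- *That all baseline data go unused.* Socioeconomic status, gender and BMI are planned moderators at level two, so they enter at least the moderation models. Pretest intake is the main item not committed; age is also uncommitted.
- *That the attitude contrast is biased.* This needs loss related to intake differently by arm, or an effect that varies with intake. The control session has the same duration and also uses reading and writing, and the posttest comes only one week after the intervention. Placing the whole allowance before posttest is an extreme case, because the allowance covers all follow-ups.
- *That the mediation analysis fails in the same way.* Its structural equation model also contains food intake, so these pupils contribute if pretest intake is included. The plan does not say whether it is.

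It is also fair that the bias is small beside sampling error. At r = -0.4 in the extreme case it is 0.032/0.090 = 0.36 of an SE with clustering ignored, and a smaller fraction with clustering.

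Finally, the precision gain is ordinary covariate adjustment. It should not be presented as recovery of missing data.

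**Conclusion.** The point holds as a minor, free improvement. On the natural reading of Measurements there is no attitude pretest, and Statistical Analysis does not commit pretest intake to the attitude models.

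The more dependable gain is precision: about 2%, 4-5% and 7-8% off the SE at |r| = 0.2, 0.3 and 0.4, less with classroom clustering. The conditional gain is protection against bias. With 5% lost before posttest that is 0.008-0.013 SD. In the extreme case of 16.7% lost with a 3:1 gradient in one arm only, it is 0.024-0.040 SD; steeper or opposing gradients would give more. If loss is random, or depends on intake equally in both arms, and the effect does not vary with intake, there is no such bias.

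The correlations, loss patterns and ICCs are all assumptions. The documents show no differential loss, so they support neither a finding of bias nor one that the missing-data method is wrong. The point concerns objective 3; for mediation it is only a request to state that pretest intake is included.

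**What to change.** In Statistical Analysis, add for the attitude outcomes:

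> Every attitude model will include pretest healthy and unhealthy intake as predictors of the attitude measures, with their own distribution modelled and their means held equal across arms, so that all randomised pupils with a pretest contribute. This is fixed before outcome data are inspected.

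The equal-means condition matters: with free arm means the precision gain almost disappears (0.0894 against 0.0898), whereas intake as a covariate gives 0.0833. Pupils with no attitude score then enter through the intake distribution; they still bring no direct information on attitude.

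Keep gender, socioeconomic status and BMI as the planned moderators, and add age if it is collected at pretest. State the occasion at which these characteristics are recorded. Include pretest intake in the mediation model as well.

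Cost: a sentence or two of analysis text and a few lines of model code. No new data are needed.

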#### BUDGET

Concept	Amount
Contract for a research assistant with a degree in psychology on a part-time basis (25 hours per week).	20,000
Travel and per diem expenses for researchers [name] and [name] for coordination and adaptation of the intervention materials for Spanish adolescents.	6,100
Incentive vouchers for participants. Vouchers will be raffled among the participants in each classroom to encourage participation. These will have a value of 20 euros and can be exchanged in shopping centers. Two vouchers will be raffled in each of the approximately 30 classrooms.	1,200
Trips to schools.	1,100
Expendable materials, such as markers and paints for intervention activities, which will be given to the adolescents.	1,600
Total	30,000
QUARTERLY WORK PLAN	1 2 3 4
1. Adaptation of the materials for Spanish adolescents	x
2. Acquisition of materials	x
3. Training the research staff on the procedures	x
4. Contacting schools and obtaining permissions	x
5. Application of pretest and intervention measures	x x x
6. One-week and three-month follow-ups	x x
7. Merging and cleaning of databases	x
8. Statistical analysis of data	x x
9. Writing the final report and scientific manuscripts	x
10. Dissemination and transference in conferences, participating schools, and society in general	x

